- 5- The Data Management Team will be responsible for ensuring that no one in the project can link the sample IDs with the person IDs and that no one can use the names database except the PDM and others listed in #4 above. Person ID's will not be released for use in other projects.
- 6- The data server will keep a log file/data audit trail that will indicate the time/date and identify for every access to the data files. No one outside the Data Management Group will be able to modify any data on the server, and unauthorized persons will not be able to access any of the data files.
- 7- Each computer, Smartphone, or smart telephone with project data will have a separate password. The PDM is responsible for controlling these permissions, and she/he is the only one that can change this. Also, each database will have an access system with user names and passwords that will control the level of access and permissions for each user. The DOLF Project Manager will be responsible for managing access to the Microsoft Azure database.

24. 8.1 Future Use of Stored Specimens

Residual specimens (serum, blood smears) will be maintained after the study is completed for future research on infectious diseases. Samples will be stripped of unique identifiers and stored in endemic country laboratories or in the PI's laboratory at Washington University. Sequencing will be performed with DNA isolated from a small number of stool or blood samples to detect and characterize worm parasite DNA (blood or stool) and bacterial DNA (stool). The samples will be deidentified prior to any sequencing procedures. In addition, all human DNA sequences will

be filtered out prior to bioinformatic analysis and no genetic testing of humans will be performed.

25. 9 INFORMED CONSENT PROCESS

We will follow procedures outlined in the DHHS Regulation on Informed Consent 45 CFR Part 46 - Subpart A, 46.116 (<http://www.hhs.gov/ohrp/humansubjects/guidance/45cfr46.htm#46.116>).

Informed consent is a process that is initiated prior to the individual's agreeing to participate in the study and continuing throughout the individual's study participation. Study physicians will read the consent script (with potential risks and benefits) in a locally understood language to subjects and their families and leave a copy of this with each family. The consent document will be reviewed and approved by project IRB's prior to initiation of the study. Study physicians will discuss risks and possible benefits of participation in this study with subjects and their families. Study physicians will explain the purpose of the study to subjects and answer any questions that may arise. The subjects may withdraw consent at any time throughout the course of the study. The rights and welfare of the subjects will be protected by emphasizing to them that the quality of their medical care will not be adversely affected if they decline to participate in this study.

26. 9.1 Informed Consent/Assent Process (in Case of a Minor or Others Unable to Consent for Themselves.

Inclusion of minor children in community surveys will require consent from at least one parent plus assent of the child.

Human studies for this project are pending at FWA registered institutional review boards at Washington University ([name]) and at IRB of the University of Liberia, Monrovia ([name]); no human studies will be conducted prior to approval by both IRBs.

Participants will be re-consented with a revised informed consent document that includes a summary of progress on disease elimination (data findings) to date as well as a description of the survey procedures (similar to the previously used informed consent).

27. 10 LITERATURE REFERENCES

1. Michael, E., D.A. Bundy, and B.T. Grenfell, *Re-assessing the global prevalence and distribution of lymphatic filariasis*. Parasitology, 1996. **112 (Pt 4)**: p. 409-28.
2. Ottesen, E.A., *Lymphatic filariasis: Treatment, control and elimination*. Adv Parasitol, 2006. **61**: p. 395-441.
3. Ottesen, E.A., et al., *Strategies and tools for the control/elimination of lymphatic filariasis*. Bull World Health Organ, 1997. **75(6)**: p. 491-503.

4. Ottesen, E.A., et al., *The global programme to eliminate lymphatic filariasis: health impact after 8 years*. PLoS Negl Trop Dis, 2008. **2**(10): p. e317.

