3 OBJECTIVES

To conduct population-based field studies to determine the relative cost and efficacy of annual vs. semiannual MDA for control and elimination of onchocerciasis and lymphatic filariasis.

1. We will test the hypothesis that twice annual MDA is superior to annual MDA for eliminating lymphatic filariasis.
2. We will test the hypothesis that twice annual MDA is superior to annual MDA for controlling soil transmitted helminth infections and onchocerciasis.
3. ***Following conclusive results on the first objectives that annual MDA is as effective as semiannual MDA for LF, oncho and STH, we will conduct an additional survey to determine long term (7 year) impact of continued MDA on onchocerciasis, LF, and STH in two areas.***

13. 4 STUDY DESIGN

(Please read this section together with Section 5, “Study Population”)

The project is comprised of repeated annual cross-sectional surveys in sentinel communities before and after initiation of mass drug administration for LF. MDA (standard regimens recommended by WHO) will be provided by government health officials. Data collection will include demographic data, history of lymphedema, scrotal swelling (hydrocele), acute filarial fever or adenolymphangitis, prior treatment for LF. Information on the presence of onchocercal nodules as well as on onchocercal skin and eye disease will be also recorded. Nodules will be assessed by superficial palpation. Blood samples will be collected from systematically sampled households. Blood will be tested for filarial antigenemia with one or more of the following: the BinaxNow Filariasis card test (also known as ICT), the Alere Filariasis Test Strip, and the TropBio test. Blood will also be tested for onchocerciasis (serology testing). Blood from persons with positive filarial antigen tests will also be tested for microfilaremia (*W. bancrofti* MF in the blood, see Section 6 below for methods). Two skin snips will be examined for microfilaridermia (*O. volvulus* MF in the skin, see Section 6 below for methods). Stool examinations will be performed for diagnosis of STH infections and schistosomiasis (*S. mansoni*), and urine will be tested for *S. hematobium*. *Note that not all tests will be performed on all samples (blood, stool and/or urine).*

Safety oversight: Study personnel will monitor subjects for adverse events related to blood collection. No medical monitor or DSMB is needed for this minimal risk, non-intervention study.

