Time to collect specimens: Most participants in the community will only be studied once (demographic data, blood, skin snips, stool and urine samples). Thus, the **duration** of subject participation will be one day.

Parameters and criteria for assessing the impact of MDA:

Blood tests for *Wuchereria bancrofti* infection: The Binax Now Filariasis card test, the Alere Filariasis Test Strip, and the TropBio antigen test (with MF testing of antigen positive subjects). We are using

these tests as measures of LF endemicity. The antigen tests detect antigen released from living adult filarial worms potentially capable of resuming MF production in the future. The filarial antigen tests are much more sensitive for infection in treated subjects than tests for microfilaremia. However, antigen tests may remain positive for years after treatment has cleared microfilaremia. The antigen tests will be performed on blood from individual residents 5 years of age and older. This will be done by sampling populations in sentinel sites (villages) to produce N of 400-500 per site. There will be several sentinel sites for each treatment zone (annual vs. twice annual MDA). The sample size number per sentinel site is close to the overall minimum target sample size of 335 needed to show that the filarial antigen rates are less than 2% (with 95% confidence and 80% power, assuming an expected rate of 0.5%, which is an LF elimination target). While all subjects will be tested with the Binax Now Filariasis card test, not all blood samples will be tested with the Alere Filariasis Test Strip and the TropBio antigen test. The purpose of parallel antigen testing of a subset of blood samples is to compare the performance of these three filarial antigen tests.

Subjects with positive filarial antigen tests will be tested for microfilaremia with 60 µl night thick blood smears collected by finger prick at night. Night blood samples are needed for microfilaria detection, because the parasites only circulate in peripheral blood at night.

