20. 7.2 Sample Size Considerations

Except as otherwise noted, all sample sizes in this protocol were calculated using a binomial power calculator (using alpha = .05, two-tailed tests, and power = .80). These sample sizes were chosen to provide confidence that measured prevalence rates will be below specified limits based on assumptions regarding true prevalence rates. The sample size analysis considered various contingencies to assess robustness of the sample size estimates (see Appendix).

Note: Sample size considerations for community surveys for demonstrating that prevalence rates are below pre-defined targets for antigenemia, microfilaremia, microfiladermia, schistosomiasis, and STH infections are provided in Section 4, above, and this is not repeated here.

21. 7.3 Participant Enrollment and Follow-Up

This project aims to enroll at least 3,200 subjects per year in Foya District and 2,000 subjects per year in Maryland County. Study areas will have cluster surveys of approximately 400-500 people per 4 sentinel site (4 sites each in the annual and semiannual MDA areas). The community/household surveys are cross-sectional with no follow-up planned.

22. 7.4 Analysis Plan

The following outcome variables will be collected and treated as binary variables: Microfilaremia, microfiladermia, filarial antigenemia and antibody, and stool/urine parasites (separate analyses for *Ascaris*, *Trichuris*, schistosomes, and Hookworm). Microfilaria counts (recorded as MF/60 μ l blood), microfiladermia counts as MF/mg skin, nodules as nodules per person, and stool egg counts for each species (recorded as eggs/gram of feces or eggs/ml urine) will be taken as count variables.

Data will also be collected for demographic characteristics and covariates including age, gender, and history of lymphedema, scrotal swelling (hydrocele), and prior treatment for LF. For demographic characteristics variables, descriptive statistics will be examined for the individuals who participate in the trials by sentinel site (village) and over years of observation. Frequency will

be tabulated for categorical variables. Descriptive statistics (mean, median, range and standard deviation) will be obtained for continuous variables.

Impact of MDA on study outcome measures

1. Testing the primary hypothesis

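### A sample of 335 does not give 80% power to show antigenemia below 2% at a true 0.5%: exact power is 76% one-sided and 50% under the two-tailed default

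*Combined protocol and SAP*

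**What the plan says.** Section 4 (Study Design), under the parameters for assessing the impact of MDA, gives the only sample-size statement for the 2% antigen target in the visible text. It names an "overall minimum target sample size of 335 needed to show that the filarial antigen rates are less than 2"%. The conditions attached to that figure read "with 95% confidence and 80% power, assuming an expected rate of 0.5"%. The section sets this beside the plan for "sampling populations in sentinel sites (villages) to produce N of 400-500 per site" and calls the two numbers close. Sampling is by household: "Blood samples will be collected from systematically sampled households".

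Section 7.2 says that, unless otherwise noted, sample sizes come from a binomial power calculator "using alpha = .05, two-tailed tests, and power = .80". For prevalence targets it refers the reader back to Section 4. It adds: "The sample size analysis considered various contingencies to assess robustness of the sample size estimates (see Appendix").

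Section 7.3 plans "at least 3,200 subjects per year in Foya District and 2,000 subjects per year in Maryland County", with surveys of "approximately 400-500 people per 4 sentinel site (4 sites each in the annual and semiannual MDA areas"). The continuation survey (Section 4, Continuation Activities) plans 2,500 people in Maryland and 3,200 in Lofa. Section 2.2 says this survey will establish whether the elimination targets, including antigen below 2%, have been met.

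**The concern.** A sample of 335 looks too small for the stated operating characteristics. At 2% one expects 6.7 positives in 335 (335 x 0.02), and at 0.5% about 1.7 (335 x 0.005). With counts this low, the cutoff that protects the 5% error rate is strict, and a population that is truly at 0.5% can easily exceed it by chance.

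Three things that the calculation needs are also left open:

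- **Sidedness.** The claim is directional, but Section 4 does not say that it departs from the two-tailed default.
- **Unit.** 335 is called an overall minimum, yet it is compared with the number per site.
- **Clustering.** No design effect accompanies the figure in the visible text, although the Section 7.4 model expects correlation within household and site.

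At stake is how a result that fails to show antigenemia below 2% is read. If the sample is thought to have 80% power when it has 76% or 50%, a failure caused by sample size may be taken as evidence that the target was missed. Section 4 says the findings will go to the Ministry of Health to support its decisions on continuing or stopping MDA.

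**Working it through.** **Inputs.** Threshold p0 = 0.02, true rate p1 = 0.005, 95% confidence, 80% power and n = 335 (Section 4). Alpha 0.05 two-tailed by default (Section 7.2). Planned n per site 400-500 (Sections 4 and 7.3). Independence is assumed until step 5.

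**1. Reproducing 335.** The usual one-sample normal formula is n = [z_a √(p0(1−p0)) + z_b √(p1(1−p1))]² / (p0−p1)².

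- One-sided: (1.645 x 0.1400 + 0.842 x 0.0705)² / 0.015² = 372.9, so 373.
- Two-sided: (1.960 x 0.1400 + 0.842 x 0.0705)² / 0.015² = 495.1, so 496.

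Neither gives 335. A precision formula with no power term does: 1.96² x 0.02 x 0.98 / 0.015² = 334.6. This suggests that the power term was left out, but that is an inference; the documents do not give the formula.

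**2. Exact power at 335.** Let X be the number of positives. The survey shows a rate below 2% if X ≤ c, where c is the largest value with P(X ≤ c | n, 0.02) ≤ 0.05 (one-sided) or ≤ 0.025 (two-tailed). Power is P(X ≤ c | n, 0.005).

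| c | Error at 2% | Power at 0.5% |
|---|---|---|
| 0 | 0.12% | 18.7% |
| 1 | 0.90% | 50.05% |
| 2 | 3.58% | 76.4% |
| 3 | 9.65% | 91.1% |

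One-sided the cutoff is 2 and power is 76.4%. Two-tailed the cutoff is 1 and power is 50.05%. Allowing 3 positives exceeds 80% power, but the error is then 9.65%.

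**3. Sample size that does reach 80%.**

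- One-sided: 386 (c = 3, error 4.95%, power 87.0%). No smaller n reaches 80%, and power does not fall below 80% at larger n.
- Two-tailed: 436 reaches it first (c = 3, 82.4%), but power is below 80% again from 460 to 508. It stays at or above 80% from 509 (c = 4, 88.6%).

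**4. Planned site sizes, independent observations.**

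| n | One-sided | Two-tailed |
|---|---|---|
| 400 | 85.8% | 67.7% |
| 450 | 81.0% | 81.0% |
| 500 | 89.2% | 75.8% |

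From 400 to 500 the one-sided minimum is 80.5% (n = 455). Two-tailed, only n from 436 to 459 reaches 80%, which leaves 101 − 24 = 77 of the 101 values below it. The lowest is 62.9% (n = 435).

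**5. Clustering.** Dividing n by the design effect gives an approximate effective sample. One-sided, a site needs an effective 386, so it tolerates a design effect of 400/386 = 1.04 or 500/386 = 1.30. At an assumed design effect of 1.5, the effective n is 267 to 333 and one-sided power lies between 54% and 79% (61% and 77% at the two ends of the range). The documents give no design effect, so 1.5 is only an illustration.

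**6. Treatment zones, if the two zones in an area are equal in size.** Maryland has 2,000/2 = 1,000 per zone: power 99.8% one-sided and 99.5% two-tailed. Foya has 3,200/2 = 1,600: above 99.9% for both. The design effects that still leave 80% power are:

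- Maryland: 1,000/386 = 2.59 one-sided, 1,000/509 = 1.96 two-tailed.
- Foya: 1,600/386, about 4.1, one-sided; 1,600/509 = 3.14 two-tailed.

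**7. Enrolment against site size.** Read as 4 + 4 = 8 sites per area, Section 7.3 needs 8 x 400 = 3,200 to 8 x 500 = 4,000 people. Foya's 3,200 fits. Maryland's 2,000 does not, and neither does the continuation survey's 2,500 if it keeps the same sites.

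**The case against.** **The claim is directional, so 50% is the harsher reading.** Section 7.2 allows for exceptions, and a two-sided mid-p or likelihood-ratio test would use c = 2 and give 76.4%. This is fair as far as it goes, but Section 4 notes no exception to the two-tailed default, and 76.4% still misses 80%.

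**The one-sided gap is 3.6 points and partly reflects discreteness.** Power moves in a sawtooth: 79.3% at 313, 76.4% at 335, 69.7% at 385, 87.0% at 386. Section 7.2 does not say that its binomial calculator was exact, and a one-sided arcsine approximation asks for only 306. That might explain a figure near 335 but does not justify it: the approximation is anti-conservative here, and no n below 386 reaches 80% by the exact test.

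**Nobody plans to survey 335 people.** This stands. Sites are planned at 400-500, areas at 2,000 or more, and the continuation survey at 2,500 and 3,200. Section 7.4 specifies no site-level test against 2%; it models village trends and time to target. The model also handles correlation in the analysis, though that does not adjust the sample size.

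**The Appendix may cover robustness.** It may lie in text removed before review, so its absence is not held against the plan. No robustness check could make 335 deliver 80%.

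**The Maryland comparison depends on an unclear phrase.** This stands too. 2,000 also equals 4 x 500, and the village counts in Section 2.2 (16, and 26 in Lofa) and Annex 1 (32) suggest that a site may not be a single village. It is a point to reconcile, and the power finding does not depend on it.

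**Conclusion.** The concern holds. The stated combination of n = 335, 95% confidence and 80% power is wrong on either sidedness. At a true 0.5%, a survey of 335 would fail to show a rate below 2% in 23.6% of cases one-sided, or 49.9% two-tailed, against the 20% implied.

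The consequence is moderate. What fails is the stated figure and any site-level claim built on it; total enrolment is adequate. One-sided and without clustering, the planned site sizes suffice. Under the two-tailed default, or with modest clustering, most or all of that margin goes. Zone totals are adequate under simple random sampling and tolerate substantial design effects.

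The power figures rest on the exact binomial test and independent observations. The zone figures also assume equal zones. The precision-formula origin of 335, the design effect of 1.5 and the eight-site reading are respectively an inference, an assumption and an interpretation; the main result needs none of them.

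**What to change.** 1. In Section 4, state whether the below-2% claim is one- or two-sided, which test and cutoff it uses, and whether it is made per site or per treatment zone.
2. Replace 335 with 386 (one-sided exact) or 509 (two-tailed exact), before a stated design effect. Alternatively, keep 335 as a precision figure and remove the 80% power label.
3. Make the below-2% claim per treatment zone, with confidence limits adjusted for clustering by household and village. The existing zone totals support this up to the design effects in step 6 of the working.
4. Reconcile Maryland's 2,000 (Section 7.3) and 2,500 (continuation survey) with 400-500 per site, and state the number of sites per area.

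These are changes of wording and need no extra participants. The cost is a less favourable stated minimum and giving up any below-2% claim for single sites.

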DOLF studies in Liberia have provided some of the most complete data on the impact of community MDA regimens for LF and other NTDs. These studies have shown that 3 years of MDA had significant impacts on LF, STH and onchocerciasis prevalence in Liberia and other study sites. However, three years of MDA was not sufficient to meet elimination targets for those infections. An additional survey in the Maryland district will provide further data on the rate of decline of filarial antigenemia prevalence following MDA in Africa and on the effects of additional rounds of MDA on onchocerciasis and on STH prevalence and intensities. Three of these study areas had very high STH prevalence at baseline (two in Liberia and one in DRC), and continuation of measuring the impact MDA through 7 years after initiation will prepare these areas as potential sites for later studies of the efficacy of school-based deworming or other maintenance strategies to prevent the rebound of STH following cessation of MDA for LF.

In the last three years, annual MDA has been administered by the the NTD team of the Ministry of Health (MOH) in Lofa and by MOH/COUNTDOWN in Maryland. At a follow-up visit in 2019 by Liberian DOLF team members, all 16 study villages had received MDA. In Lofa County, MDA was conducted through the MOH alone, and the DOLF team recorded that not all of the 26 study villages in Lofa received MDA in 2018.

The proposed additional survey will provide data on long-term impact of MDA and support endgame research to understand how many rounds of MDA are needed to achieve elimination of LF and oncho and control of STH infections. The elimination targets for LF are <2% prevalence of antigen (assessed with FTS) and <1% prevalence of microfilaria (assessed with thick blood smear). The elimination target for onchocerciasis is <5% microfilaria in the skin (assessed by skin snip). The proposed survey will determine if these targets have been reached, and will answer the question of how many additional rounds of MDA are needed to achieve elimination targets. The answer to this question is critical for global elimination programs and may inform global policies.

10. 2.3 Potential Risks and Benefits / Potential Risks

Immediate risks

11. 2.3.1 Potential Risks

This research includes risks associated with collection of blood by finger prick and of skin snips (superficial skin biopsies collected by corneoscleral biopsy punch).

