The primary hypothesis is that twice annual MDA is superior to annual MDA for eliminating LF. The binary outcome variables used to test this hypothesis include microfilaremia and antigenemia. The model which is being used will fit a linear trend over time within each village. The mean slope across villages within each treatment group will then allow estimates of time to target levels for control (microfilaremia < .5% and antigenemia < 2%) for a selection of baseline prevalences. To illustrate the analysis strategy, we use antigenemia as an example.

The antigenemia prevalence will be expressed as the filarial antigenemia rate (proportion of examined individuals with filarial parasite antigenemia detected with the Binax Now Filariasis card test. If Alere stops selling the card test, we may need to switch to their antigen strip test as the primary antigen test in later years of the project. To estimate the effect of MDA on antigenemia prevalence, we will tabulate mean rates of antigenemia across the four sentinel sites from each treatment zone (annual vs. twice annual MDA) over years of observation including the baseline. A generalized linear mixed model (GLMM) with a logistic link function will be used to account for the correlation of observations clustered within the same household from the same sentinel site. The model to estimate the difference in the odds of antigenemia includes treatment regimen and year of observation, and interaction between treatment regimen and year of observation. Some covariates that will be adjusted for in the analysis include sentinel sites, history of lymphedema, scrotal swelling (hydrocele) and prior treatment for LF as well as demographic variables of interest. Modeling will be performed with use of PROC GLIMMIX in SAS 9.2. CONTRAST statements will be used to test the significance of the log odds of antigenemia between the two treatment regimens at each year of observation. The difference of slope of rate decrease between the two regimens over the years of observations will also be tested with CONTRAST statements in PROC GLIMMIX. The resulting estimates will be converted to odds ratios with 95% confidence interval calculated from the robust estimator of variance. The other binary outcome variables (e.g., microfilaremia and microfilaridemia) will be analyzed with the same technique.

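### The 335-person minimum and its 95% confidence and 80% power assume independent people, and the visible plan gives no cluster-adjusted limit for claims that prevalence is below target

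*Combined protocol and SAP*

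**What the plan says.** Section 7.2 states that, except where noted, "all sample sizes in this protocol were calculated using a binomial power calculator", with alpha 0.05, two-tailed tests and power 0.80. Section 4 gives the one worked figure: "The sample size number per sentinel site is close to the overall minimum target sample size of 335", a number "needed to show that the filarial antigen rates are less than 2% (with 95% confidence and 80% power", with an assumed true rate of 0.5%. The planned number is 400 to 500 per sentinel site.

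The same plan describes clustered data. Section 4 draws blood samples from households chosen systematically. Section 7.3 describes the surveys as cluster surveys, with four sentinel sites in each MDA zone. Section 7.4 fits a mixed model to "account for the correlation of observations clustered within the same household from the same sentinel site". That model serves the regimen comparison and the slopes. Section 7.4 also uses mean village slopes to estimate the time to reach the targets.

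For the continuation survey, Section 2.2 sets targets that include antigen below 2% and skin microfilariae below 5%, and says "The proposed survey will determine if these targets have been reached". The Continuation Activities text plans 2,500 people in Maryland and 3,200 in Lofa, with findings shared to support decisions on continuing or stopping MDA. No section in the visible text states how an upper limit on prevalence, or a below-target decision, will be computed.

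**The concern.** People in one household share exposure, and people in one village share exposure and treatment coverage. Section 2.2 records that not all 26 Lofa study villages received MDA in 2018. Positive correlation makes the count of positives more variable than the binomial allows. A binomial upper limit is then too low, and an area sitting exactly at the target is declared below it too often. If the limit is widened to allow for this, the cost appears as lost power.

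The question is practical. The last Lofa survey found skin microfilariae in 4% (annual) and 5% (semiannual), against a target of below 5%. A borderline result is therefore realistic, and it would inform decisions about MDA.

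**Working it through.** **Inputs from the documents.** Limit p0 = 2%, expected rate p1 = 0.5%, 95% confidence, 80% power, n = 335, and 400 to 500 per site (Section 4). Alpha 0.05 two-tailed (7.2). Village counts of 16, read from context as Maryland, and 26 in Lofa (2.2). Continuation enrolment of 2,500 and 3,200.

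**Assumed, because the documents give no values.** 5 or 8 people tested per household with household ICC 0.1 or 0.2. Between-village CV of prevalence 0.35, 0.5 or 1.0.

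**1. The plan's own figure.** The usual one-sample formula is n = [(z_α√(p0q0) + z_β√(p1q1)) / (p0 − p1)]².
- One-sided: [(1.645 × 0.1400 + 0.842 × 0.0705) / 0.015]² = 373.
- Two-sided (1.960 in place of 1.645): 496.
- Nearest match, a one-sided average-variance shortcut: (1.645 + 0.842)² × (0.0196 + 0.004975)/2 / 0.015² = 338.

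So 335 is not reproduced from the stated two-tailed setting. None of these formulas has a clustering term. With independent people, the exact one-sided rule at 335 accepts up to 2 positives and gives confidence 96.4% and power 76.4%. The exact two-tailed rule accepts up to 1 and gives 99.1% and 50.1%.

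**2. Site level with household clustering.** Each household's positives are beta-binomial, and households are summed exactly. The design effect is 1 + (m − 1) × ICC:
- 5 per household: 1.4 (ICC 0.1) and 1.8 (ICC 0.2).
- 8 per household: 1.7 and 2.4.

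The binomial cutoff is the largest count with probability at most 5% (or 2.5%) at p0 under independence. The cluster-valid cutoff is the largest count meeting 5% under the clustered distribution.

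| N | One-sided cutoff | False claim, independent | False claim, clustered | Power with cluster-valid 5% cutoff | False claim, clustered, 2.5% tail |
|---|---|---|---|---|---|
| 335 | 2 | 3.6% | 6.3–13.4% | 37–56% | 2.1–6.3% |
| 400 | 3 | 4.1% | 7.1–14.2% | 53–68% | 2.8–7.8% |
| 450 | 3 | 2.0% | 4.0–9.8% | 48–79% | 4.0–9.8% |
| 500 | 4 | 2.8% | 5.3–11.6% | 60–74% | 2.3–6.6% |

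At 450 the whole-number cutoff happens to be conservative, and it is the same for both tails. I also checked every N from 335 to 500. The 5% error and 80% power are met together only at 432 to 434 people, and only under the mildest assumption (5 per household, ICC 0.1), with power just over 80%.

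The planned numbers leave limited room: 400/335 = 1.19 and 500/335 = 1.49. Inflating 335 by a design effect of 1.2, 1.5, 2 or 3 gives 402, 503, 670 or 1,005.

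**3. Area level, villages treated as a sample of the area.** Village ICC = CV² × p/(1 − p). At p = 2% this is 0.0025, 0.0051 and 0.0204. At p = 5% it is 0.0064, 0.0132 and 0.0526. Maryland is taken as 16 × 156 = 2,496 and Lofa as 26 × 123 = 3,198. The table gives false below-target rates for a one-sided 5% binomial rule with true prevalence exactly at target.

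| Area, target | Cutoff | Independent | CV 0.35 | CV 0.5 | CV 1.0 |
|---|---|---|---|---|---|
| Maryland, 2% | 38 | 4.7% | 7.7% | 11% | 22% |
| Lofa, 2% | 50 | 4.1% | 6.3% | 8.6% | 18% |
| Maryland, 5% | 106 | 4.4% | 11% | 17% | 31% |
| Lofa, 5% | 139 | 4.7% | 10.5% | 15% | 28% |

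**4. Area level, claim limited to the study villages.** The villages then act as strata. With village prevalences held fixed around a 2% mean, the Maryland rate stays at about 4.5 to 4.7% at all three CVs. Only household clustering within villages would raise it.

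**The case against.** The strongest reply is that the quoted text is about planning. No section says that a binomial limit will be applied to the survey data. If the analysts use a cluster-adjusted limit, confidence stays near 95% and only power suffers. This stands, and it rules out saying that the plan's analysis is binomial. It does not remove the point: the stated confidence and power then still fail together, and the plan still gives no limit.

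Other parts of the reply also stand:
- The 95% confidence is stated only for antigen below 2%, and 335 is compared with the number per site. The plan makes no such promise for skin microfilariae or for area totals.
- No random selection of villages is described, and Section 4 calls them sentinel communities. The area-level inflation holds only if the claim reaches beyond them.
- Under the two-tailed alpha of 7.2, several clustered false-claim rates stay below 5%, although most exceed the 2.5% that such a rule implies.
- Planned site numbers exceed 335. That helps power, but extra people do not correct an unadjusted limit.
- Section 7.2 refers to contingencies in an Appendix that the reviewed text does not show, so it cannot be said that clustering was considered nowhere.

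A reader might infer that the true confidence is in practice about 80 to 93%. The documents do not support that. By normal approximation it needs design effects of about 1.2 to 3.8, and no ICC, CV or household size is given. A reader might also infer that clustering is ignored throughout, but 7.4 models it for the regimen comparison.

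**Conclusion.** The point holds as a gap between the stated operating characteristics and the design, and as a missing analysis rule. Under the assumed household clustering, an unadjusted one-sided rule has a false below-2% rate of about 5 to 14% at 335, 400 and 500 per site (4 to 10% at 450). With 2.5% in the tail the rate is about 2 to 8% (4 to 10% at 450). Keeping the error at 5% leaves power of about 37 to 74% (48 to 79% at 450). The stated pair is therefore not delivered, apart from the three-person window noted in the working.

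At area level, the false-claim rate is about 6 to 22% for the 2% target and 10 to 31% for the 5% skin target, if villages are a sample of the area with CV 0.35 to 1.0. If the claim covers only the study villages, between-village variation adds no sampling error.

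The direction is certain for any positive correlation. The sizes rest on assumed values. The change should be made because the continuation survey turns on this claim.

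**What to change.** - **Sections 4 and 7.2:** state that 335 and its 95% and 80% figures assume independent people. Give the formula, sidedness and decision rule behind 335, and restate confidence and power over a range of design effects.
- **Section 7.4:** state that every below-target claim uses a cluster-adjusted one-sided 95% upper limit, for example Korn-Graubard limits on the effective sample size, which suit few positives.
- **Section 7.4, unit of clustering:** use the household for a claim about a single-village site, where a village-level variance cannot be estimated. Use the village as primary sampling unit for area claims that generalise beyond the study villages. Say which population each area claim covers.
- **Reporting:** give the design effect for each area and outcome.

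The cost is plan wording and a survey-procedure analysis, with household and village identifiers carried into the analysis file. No added enrolment is needed to make the claim valid. Limits will be wider, so a borderline area may not be declared below target.
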